5. ANALYSIS POPULATIONS

The following analysis sets are planned for this study (see Table 2 for a complete comparison of these analysis sets):

Table 2: Comparison of Different Analysis Sets

	Consented	Randomized	Treated by Either Arm	Analyzed as Treated	Analyzed as Randomized	Eligibility Met	Met Wound Criteria*	Had Primary Endpoint Assessment on Day 6-9	No Disqualifying** Protocol Deviations
Safety Analysis Set (SAS)	✓		✓	✓					
Intention to Treat Analysis Set (ITT)/Full Analysis Set (FAS)	✓	✓			✓				
Modified Intention to Treat Analysis Set (mITT)	✓	✓	✓		✓	✓	✓	✓	
Per-Protocol Analysis Set (PP)	✓	✓	✓	✓	✓	✓	✓	✓	✓

* Has no more than 2/3 of the wound bed surface area considered to be clean, healthy, viable wound bed as determined at the baseline measurement confirmed with 3D images by an independent assessor

** No disqualifying protocol deviation(s) or missing primary endpoint data that would impact the interpretation/analysis of the primary endpoint

5.1. Safety Population

Safety Analysis Set includes all randomized Subjects who received either VFCC and NPWTi-d or collagenase ointment for any length of time. Subjects will be analyzed as treated.

5.2. Intent-To-Treat Population

The intent-to-treat (ITT) analysis set includes all randomized Subjects. Subjects will be analyzed as randomized.

5.3. Full Analysis Set

The Full Analysis Set (FAS) will be defined as all randomized Subjects who have received treatment, either VFCC and NPWTi-d or collagenase ointment for any length of time. Subjects will be analyzed as randomized. See Section 6.3.1 on situations where missing data will be imputed in the FAS.

5.4. Modified Intention-to-Treat Population (mITT)

Modified intent-to-treat (mITT) will include all randomized Subjects with the following:

- i. met all the inclusion criteria and none of the exclusion criteria,
- ii. had no more than 2/3 of the wound bed surface area considered to be clean, healthy, viable wound bed as determined at the baseline measurement confirmed with 3D images by an independent assessor,
- iii. received either the V.A.C. VERAFL0 CLEANSE CHOICE™ Dressing and NPWTi-d or collagenase ointment,
- iv. had the primary endpoint assessment on Day 6-9

5.5. Per-Protocol Population

Per-Protocol (PP) analysis set will include all Subjects in the mITT who had no disqualifying or major protocol deviation(s) that would impact the interpretation of the primary endpoint (i.e. change in percent of wound surface area considered clean, healthy and viable). Subject data will be analyzed in the arm to which they were randomized and treated.

Situations and deviations that lead to an exclusion from the PP analysis will be defined and justified in a blinded fashion. In addition, documentation will be made of these data classification decisions prior to database lock.

6. GENERAL STATISTICAL CONSIDERATIONS

- Data processing, tabulation of descriptive statistics and calculation of inferential statistics will be performed primarily using SAS version 9.4 or higher (SAS Institute, Cary, NC). If the use of other software is warranted, the final report will detail software deployed along with the reasons for use.
- Summaries of continuous variables will show the number of non-missing values [n], along with the mean, standard deviation, median, minimum, and maximum. In general, minimum and maximum values will be presented to the same precision as the raw data; the mean and median will be presented to one decimal place more than the raw data. Standard deviation

and confidence interval limits will be presented to two decimal places more than the raw data.

- Summaries of categorical (qualitative) variables will include the frequency and percentage of Subjects in each category. In general, the denominator for the percentage calculation will be based upon the total number of Subjects in the study population, unless otherwise specified. Percentages will be presented to 1 decimal place, except a value of zero, which will only be displayed as “0” or unless otherwise specified.
- Subjects in all the analysis sets will be summarized by treatment arm and overall.
- P-values will be presented to four decimal places. A p-value less than 0.0001 will be presented as < 0.0001 or < .0001.
- The assessment prior to the initial treatment application will be considered a baseline value. If debridement is deemed to be necessary, then the assessment directly after debridement will be used as the baseline reference.
- Percent change from baseline will be calculated using the relevant post initial dressing application value minus the baseline value.

Other ad hoc data analyses may be conducted to characterize the activity of the treatment. These additional ad hoc analyses will be decided at the time of the analysis and will be identified in the output and CSR. Other ad hoc data analyses to characterize safety and/or efficacy activity of treatment arms may be conducted. These additional ad hoc analyses will be decided at the time of analysis and will be labeled as such. Due to the exploratory nature of the analyses, no adjustment for multiplicity will be made in these ad hoc analyses.

6.1. Interim Analysis

A non-binding, unblinded interim analysis will be performed when approximately 30 evaluable Subjects have had their assessments for the primary endpoint (percent change on wound bed surface area considered to be clean, healthy, and viable from baseline to Day 6-9). The purpose of the interim analysis is to evaluate the need for early stopping due to futility, efficacy, and/or sample size re-estimation.

Details of the planned analyses to occur at interim are outlined in the interim Statistical Analysis Plan (SAP) document: CLIN-PROT-SAP-05-813629.

6.2. Determination of Sample Size

The study will randomize approximately 60 Subjects from approximately 15 sites in a 1:1 ratio to either the V.A.C. VERAFL0 CLEANSE CHOICE™ (i.e., Treatment) arm or the collagenase ointment (i.e., Control) arm. Sample size determination is based on the primary endpoint. It was estimated that slough reduced by almost 20% in the Tender Wet 24 group and 10% in the Iruxol N group in M. Konig et al.¹ Assuming a 20% increase in clean, healthy, viable wound bed surface area in the collagenase ointment group and a 40% increase in clean, healthy, viable wound bed surface area in the VFCC and NPWTi-d group, and a typical standard deviation of 22%, 23

evaluable Subjects per group would provide approximately 80% power to detect a statistically significant difference using the Wilcoxon Rank-Sum test (nQuery Advisor® 7.0).

In some circumstances, even though the investigator assessed the wound to have $\leq 2/3$ area of clean, healthy, and viable wound bed, it may not meet the requirement when assessed by the independent assessor if measured by a 3D camera. Such Subjects will be excluded from the mITT for the analysis of the primary endpoint. To allow for this possibility, plus the possibility that some Subjects may be lost to follow-up prior to their post-baseline assessment at the Day 6-9 visit, the sample size is increased to a total of 60 randomized Subjects (i.e., 30 Subjects per arm). This accounts for an approximately 23% drop out rate.

6.3. Handling of Dropouts and Missing Data

6.3.1. Imputation for Missing Efficacy and General Data

Missing efficacy data will not be imputed in the primary analysis on the changes in percent wound bed considered clean, healthy, viable tissue (%) using the mITT dataset.

Missing efficacy data involving the primary and secondary endpoints using the FAS dataset will be imputed using the next observation carried backward (NOCB) for missing baseline data and last observation carried forward (LOCF) for missing post-baseline data. Data will be imputed for the FAS dataset that are missing for the following variables: percent wound area considered clean/viable/healthy; wound area; and wound volume. The derived endpoints impacted will be change in percent of wound bed considered clean, healthy, viable tissues (%), percent change in wound area (%), percent change in wound volume (%), absolute change in total area (cm^2), absolute change in area considered clean, viable, healthy (cm^2), and absolute change in volume (cm^3). This dataset will be referred to as FAS (with NOCB/LOCF imputation).

The secondary endpoint of Physician assessment of the need for surgical debridement upon completion of study treatment up to Day 6-9 implies that assessment made prior to Day 6-9 (even on unscheduled visits) reflecting the end-of-treatment assessment will be used. In the event that this secondary endpoint or any exploratory endpoint (except the absolute change in total area, volume, and area considered clean, viable, healthy) is missing, imputation will not be carried out and all available data will be used in the analysis. All available data without imputation will be referred to as ITT (without imputation).

If wound type was missing prior to protocol version 5.0 (when I/E criteria was modified to broaden the wound types allowed in the study), the wound type will be set to "Pressure Ulcer".

Wounds with no undermining will have the percent of wound margin with undermining set to 0%. In addition, percent of wound margin with undermining initially captured as <25% will be summarized in the report as 1-<25% for clarity.

6.3.2. Conventions/Imputations for Adverse Events and Concomitant Medications.

If the adverse event (AE)/ Concomitant Medication (CM) start date is partially missing [e.g. the month of the start date is missing, or the day of the date is missing], the following conventions will be applied:

- If only the day is missing then the imputed day will be: The day of the initial dressing/treatment application if the month is the same, or the first day of the month will be used if the month differs or the imputed day results in a start date after the end date.
- If only the month is missing then the imputed month will be the month of the initial dressing/treatment application if the year is the same, or ‘January’ if the year differs.
- If both month and day are missing, then the month is imputed as the month and day of the initial dressing/treatment application. If the imputed day results in a start date after the end date, then the first day of the month will be used.

If the AE start date is missing and the end date is complete

- If the end date is on or after the date of the initial dressing application/treatment, the start date will be imputed as the date of the initial dressing application/treatment start.
- If the start date is completely missing and the end date is completely missing then the AE/CM will assume to be “on-study”, then the start date will be set to the date of the initial dressing application/treatment.
- If the start date is completely missing and end date is prior to the initial dressing application/treatment, the AE/CM will assume to be ‘prior to study’ and not be included in any summaries.

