4.1.3. Exploratory Endpoint(s)

The exploratory endpoints for this study include:

- Repeated measures of the change in percent of clean, healthy, viable tissue (%) over time, analyzing the rate of change and differences at study visits.
- Repeated measures of the percent change in total wound volume (%) over time, analyzing the rate of change and differences at study visits.
- Repeated measures of the percent change in total wound area (%) over time, analyzing the rate of change and differences at study visits.
- The absolute change from baseline to Day 6-9 upon the final dressing removal in the wound bed surface area (cm^2) considered to be clean, healthy, and viable.
- The absolute change from baseline to Day 6-9 in the total wound area (cm^2).
- The absolute change from baseline to Day 6-9 in the total wound volume (cm^3).
- Repeated measures of the absolute change in total wound volume, total wound area and viable wound area over time, analyzing the rate of change and differences at study visits.
- The percent change and absolute change of granulation tissue from baseline to Day 6-9 upon the final dressing removal
- Number of treatment applications and/or dressing changes per Subject (i.e., collagenase ointment applications versus VFCC applications); analyzed by treatment duration, wound size, and/or wound type, as appropriate.
- Total time to perform treatment applications and/or dressing changes per Subject; analyzed by wound size and/or wound type, as appropriate.
- Within-VFCC-treatment changes in the percent of wound bed surface area considered clean, healthy, viable tissue (%) at Day 2-3 and Day 4-6 study visits relative to baseline.
- Within-VFCC-treatment changes in the percent of total wound area (%) at Day 2-3 and Day 4-6 study visits relative to baseline.
- Within-VFCC-treatment changes in the percent of wound volume (%) at Day 2-3 and Day 4-6 study visits relative to baseline.

- Within-Collagenase-control-treatment changes in the percent wound surface area considered clean, healthy and viable; changes in percent wound area; and changes in percent wound volume at all study visits relative to baseline.

In addition to these exploratory endpoints, the following data will be collected from Subjects in one of the groups:

- Total number of collagenase ointment tubes used per Subject; analyzed by treatment duration, wound size, and/or wound type, as appropriate.

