Additionally, a line plot and/or scatterplot and/or boxplots showing the mean or observed percentage in the wound bed surface area considered to be clean, healthy, and viable by treatment arm over time will be generated to display the results from the analyses of the primary endpoint in the FAS, mITT and PP analysis sets.

The following supportive analyses will be conducted in the primary endpoint:

- Repeat the primary analysis on the FAS analysis set using Next Observation Carried Back (NOCB) and Last Observation Carried Forward (LOCF) method, that is, FAS (with NOCB/LOCF imputation).
- Repeat the primary analysis on the Per-Protocol analysis set

If appropriate, supportive/exploratory analyses of the primary endpoint will include:

- A proportional odds logistic regression model (ordered logit link function) with quartile or quintile groupings of the data
- Wilcoxon Rank-Sum test without adjusting for covariates like wound undermining
- Analyses comparing the treatment groups considering covariates (e.g., age, race/ethnicity, sex, and comorbidities)
- Other analyses deemed appropriate to examine unexpected interaction terms including, but not limited to, impact of the Covid pandemic.

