8.3. Exploratory Analysis

8.3.1. Tissue Typing Assessments

Tissue typing assessments will be summarized across timepoints by treatment arm and by visit based on the mITT and FAS (with imputation) analysis sets.

The variables to be summarized are as follows: Viable B/L/C/T (bone/ ligament /cartilage/ tendon); Viable fat; Granulation; Viable muscle/fascia; Non-viable B/L/C/T; Non-viable fat; Non-viable muscle/fascia; Eschar; and Slough. These variables will be summarized as percent of total wound surface area (%) and absolute area (cm²).

The composite variables to be summarized in terms of percent of total wound surface area (%) and absolute area (cm²) are:

1. clean/healthy/viable tissues (sum of the first four categories listed previously: viable B/L/C/T (bone/ligament/cartilage/tendon); viable fat; granulation; viable muscle/fascia) and
2. non-viable tissue (sum of non-viable B/L/C/T; non-viable fat; non-viable muscle/fascia; eschar; and slough).

Summaries by wound type (pressure ulcer, diabetic foot ulcer, venous leg ulcer and burn wounds) will be carried out if appropriate.

All data supporting the summaries will be provided as subject listings with all available and imputed data included.

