8.3.2. Repeated Measures Analyses

In addition, a repeated measures analysis of covariance model (ANCOVA) will be applied to analyze the endpoints of percent of wound bed clean/viable/healthy, total wound volume and total wound area. Fixed covariates of clinical site, treatment arm, wound undermining measurement, visit, and treatment by visit. If clinical site or treatment by visit is not statistically significant, then the non-significant term(s) will be removed from the model, and the updated model will be re-run. Covariance structure will be unstructured, AR(1) or TOEFL, selected based on best fit (likelihood ratio tests or based on appropriate fit statistics).

These endpoints will be summarized based on the mITT and the FAS (with NOCB/LOCF imputation) analysis sets.

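### The full-analysis-set check on the primary result rests on single NOCB/LOCF imputation, and SAP 6.3.1 leaves unclear which exploratory FAS analyses are imputed

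*SAP*

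**What the plan says.** SAP 6.3.1 leaves the primary mITT analysis unimputed. For the FAS it states that missing data on the primary and secondary endpoints "will be imputed using the next observation carried backward (NOCB) for missing baseline data and last observation carried forward (LOCF"). Its second paragraph names percent viable tissue, wound area and wound volume as the variables to fill in, and lists the derived endpoints affected.

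SAP 8.1 places this among the supportive analyses that are firmly planned: "Repeat the primary analysis on the FAS analysis set using Next Observation Carried Back (NOCB) and Last Observation Carried Forward (LOCF) method". No unimputed FAS analysis and no multiple imputation of the primary endpoint is named.

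The third paragraph of SAP 6.3.1 turns to the debridement assessment and to any exploratory endpoint other than three absolute changes. If these are missing, "imputation will not be carried out and all available data will be used in the analysis". SAP 4.1.3 lists as exploratory "Repeated measures of the change in percent of clean, healthy, viable tissue (%) over time". SAP 8.3.2, which analyses that endpoint, says: "These endpoints will be summarized based on the mITT and the FAS (with NOCB/LOCF imputation) analysis sets". SAP 8.3.3, also exploratory, uses the imputed FAS as well. SAP 8.3.1 says: "Tissue typing assessments will be summarized across timepoints by treatment arm and by visit based on the mITT and FAS (with imputation) analysis sets".

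One condition for the mITT set is that the subject "had the primary endpoint assessment on Day 6-9" (SAP 5.4). Per-Protocol is drawn from mITT (SAP 5.5).

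**The concern.** The FAS repeat is the planned analysis that shows whether the mITT result depends on leaving out treated subjects with no Day 6-9 image. It can do that only if its handling of those subjects does not add a shift of its own.

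LOCF assumes that a wound stops changing at its last image, in a trial that expects change up to Day 6-9. NOCB takes an image made on treatment as the baseline, although SAP 6 defines baseline as the assessment before the first application. This removes the change up to that image, and it also puts the wrong value into the baseline covariate of the SAP 8.1 model. A subject with no baseline image cannot meet the mITT condition of at most 2/3 viable tissue confirmed on 3D images. NOCB therefore acts only on subjects whom the FAS alone brings in.

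A repeated-measures model can use incomplete series directly, and filling them in first gives that advantage away. At stake is how far the supportive result can be trusted, not the primary test.

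**Working it through.** **1. The plan's own figure.** Inputs from SAP 6.2: means 40 and 20, SD 22, 23 evaluable per group, about 80% power, Wilcoxon rank-sum test. With p = Φ(20/(22√2)) = 0.740, Noether's formula gives n = (1.960 + 0.842)²/(6 × 0.240²) = 22.7, so 23 per group with 80.4% power. The sample size reproduces and is not in dispute. The allowance is 7 of 30 per arm (23%).

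**2. Which primary-endpoint analyses keep a treated subject without a Day 6-9 image?**
- Primary analysis (mITT): no, by SAP 5.4.
- Per-Protocol repeat: no, because it is a subset of mITT.
- FAS repeat (SAP 8.1): yes, with NOCB/LOCF.
- Repeated measures (SAP 8.3.2): the mITT version does not; the FAS version does, on imputed data as written.

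**3. LOCF in closed form.** Let s be the share of the final change already reached at the last image (an assumption), and kV and kC the subjects lost out of 30 in each arm. Then

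difference = 20 − (kV/30)(1 − s)·40 + (kC/30)(1 − s)·20.

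For three per arm and s = 1/3: 20 − 2.67 + 1.33 = 18.7.

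| Lost | s = 1/3 | s = 2/3 | s = 5/6 (late loss) |
|---|---|---|---|
| 3 per arm | 18.7 | 19.3 | 19.7 |
| 3 VFCC only | 17.3 | 18.7 | 19.3 |
| 3 control only | 21.3 | 20.7 | 20.3 |

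Seven lost per arm would give 16.9 to 19.2. That is not a forecast: the 23% allowance also covers wounds that fail the 2/3 criterion, and those have images.

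**4. NOCB.** If the next image shows a share s of the change, a VFCC subject loses 40s, which moves the difference by −40s/30: −0.4 (s = 1/3) to −0.9 (s = 2/3). A control subject moves it by +0.2 to +0.4. After covariate adjustment in the simulation below, the shifts are −0.3 to −0.5 and +0.1 to +0.3.

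**5. Simulation** (2,000 trials, 15 sites of 4 subjects). Assumptions not in the documents: baseline mean 35 and SD 18; values held to 0-100%; adjacent-visit correlation 0.6; modest site, BMI, undermining and baseline effects; all losses after Day 2-3, with 1/3 or 2/3 of the change reached by then. NOCB/LOCF and complete-case data were analysed by ANCOVA with treatment, baseline, BMI, undermining and site. The observed data were analysed with an unstructured likelihood model. Shifts are from the full-data estimate of 18.2:

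| Loss | Complete cases | NOCB/LOCF | Observed-data model |
|---|---|---|---|
| 3 per arm, random | 0.0 | −0.5 to −1.2 | 0.0 |
| 3 VFCC, random | 0.0 | −1.2 to −2.5 | 0.0 |
| 3 control, random | 0.0 | +0.6 to +1.3 | −0.1 |
| 3 VFCC from the 10 weakest early responders | +0.7 | −1.8 to −3.1 | −0.2 |
| 3 VFCC from the 10 strongest early responders | −0.8 | −0.6 to −1.8 | +0.2 |

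With weak responders lost, the rule's own shift is larger than the bias it should reveal. With strong responders lost, it points the same way as that bias and can hide it. The sampling SD of the estimate is about 5, so every shift is below one standard error.

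**6. The wording of SAP 6.3.1.** The second paragraph covers exactly the three variables that SAP 8.3.2 models. The exploratory sentence in the third paragraph excepts only the three absolute changes, so on its face it takes the repeated-measures percent endpoints out of imputation. SAP 8.3.2 and 8.3.3 follow the second paragraph. SAP 8.3.7 and 8.3.8 (granulation) follow the third. For SAP 8.3.1, the single tissue types appear nowhere among the imputed variables, yet their summaries are requested on the imputed FAS.

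**The case against.** A reader might infer that the SAP flatly contradicts itself on the repeated-measures analysis. The text does not go that far. The second paragraph of SAP 6.3.1 can be read as a rule by variable that governs every FAS analysis of percent viable tissue, area and volume, and the later sections fit that reading. The fault is an exception list that is too short. It still matters, because two programmers could build different datasets. The gap on single tissue types is real but concerns descriptive summaries.

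A carried value may also be better than it sounds. Protocol 4.4.2 asks for wound assessment before withdrawal, and Protocol 5.1 and 5.2.5 provide 3D imaging at an early-withdrawal visit. A carried image may then show the wound at the actual end of treatment. This stands: in that case LOCF does less harm, and the simulation leaves it out. Protocol 8.1.1 speaks of the last post-baseline value, which might seem to license LOCF, but the same sentence names Day 6-9, and SAP 8.1 fixes that visit.

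The sizes are small. With equal random loss of three per arm, the NOCB/LOCF root mean squared error is no worse than the model's (5.1-5.2 vs 5.35). With three weak VFCC responders lost it is somewhat worse (5.3-5.9 vs 5.1). The gain is therefore less bias, not more precision. It can be argued that a visible gap between FAS and mITT is what a sensitivity check is for. But when the gap comes mostly from the fill-in rule, it says little about dropout.

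Finally, the proposed model is not a literal repeat of the primary analysis. The repeated-measures ANCOVA in Protocol 8.3.4 was specified on mITT, lists no baseline response and allows treatment-by-visit to be dropped. That is fair, and it is a reason to let LOCF stay as a secondary run.

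**Conclusion.** The point holds as a limited one, worth considering. Every committed primary-endpoint analysis that clearly keeps treated subjects without a Day 6-9 image uses single NOCB/LOCF imputation, so the main check on missing Day 6-9 data carries a bias of its own. With three lost per arm the planned difference of 20 becomes about 18.7 to 19.7. Its direction depends on which arm loses subjects. These figures rest on assumed counts and time courses, since the documents give neither.

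Three stronger readings are not supported. The primary result is not affected, because the mITT test is unimputed. The rule does not generally favour VFCC: equal loss with equal time courses shrinks the difference, and only loss weighted towards control inflates it. Large distortions would need heavy and very unequal loss, which nothing in the documents predicts. SAP 6.3.1 is ambiguous rather than plainly contradictory.

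**What to change.** - Drop NOCB for missing baselines.
- Run the SAP 8.3.2 repeated-measures model for percent viable tissue on the observed, unimputed FAS data. Treat baseline as a response, so that subjects with a missing baseline stay in; retain treatment-by-visit; use Kenward-Roger degrees of freedom. The last matters here: in the simulation the model's plug-in standard error was 5.1 against a sampling SD of 5.35.
- Name this as the main FAS supportive analysis of the primary endpoint. Keep LOCF only as a secondary sensitivity run.
- Align SAP 6.3.1, 8.3.1, 8.3.2 and 8.3.3 on which FAS analyses are imputed, including the single tissue types.

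Optional: multiple imputation by arm, one delta-adjusted run (the model assumes missing at random), and a rule for assigning unscheduled and early-withdrawal images to visits.

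The cost is wording and a small programming change on data already collected. The FAS interval widens: the sampling SD rises from 5.0 to 5.35 with three lost per arm, and from 4.9 to 5.7 with seven. If the database is already locked, SAP 1 rules out an amendment but allows an added exploratory analysis noted in the CSR.

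One limit remains. The FAS also readmits ineligible wounds and wounds above 2/3 viable, so a difference between FAS and mITT will still not isolate dropout bias.

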### **3.1.3. Duration of Study Participation**

The duration of study participation for each Subject is as follows:

- Screening Period: up to 10 days (Day -10 to Day 0)
- Treatment Period: up to nine (9) days (Day 0 to Day 9)

The maximum participation duration per Subject is up to 19 days.

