### 7.4. AE Collection/Reporting Period

The AE collection/reporting period will begin after the Subject has been randomized. Investigators should assess for AEs at each visit. In addition, study Subjects should be instructed to report any AE that they experience to the Investigator.

All AEs, regardless of perceived relationship to study product, will be reported and recorded on the appropriate case report forms (CRFs) in a timely manner. In addition, the worsening of a medical condition previously reported in the medical history should also be recorded as an AE.

The AE description will include the nature of the experience (AE term), the start date, the end date, the severity of each sign or symptom, the seriousness of the event or experience, relationship to study treatment, the course of action taken, and the outcome of the experience. It will be indicated if the AE caused the Subject to be discontinued from the study.

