### **8.1.3. Safety Endpoints**

Treatment-emergent adverse events (TEAE) are those that first appear or worsen after the initial application of the assigned study treatment (ie, V.A.C. VERAFL™ Therapy using VFCC or collagenase ointment). Adverse events will be coded using the MedDRA dictionary.

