9.2. Adverse Events

All treatment-emergent adverse events (TEAEs), which are defined as adverse events with onset or worsening of pre-existing conditions on or after the initial dressing application through the course of the study, will be summarized. The number and percentage of treated Subjects who experienced at least one adverse event in each system organ class by preferred term will be summarized. In any given category (e.g., system organ class or preferred term), a Subject will be counted only once. The denominator for the calculation of percentages will be the number of Subjects in the Safety analysis set. The test for significant between-treatment differences will be carried out using the Fisher's exact test.

The following summary tables and listings will be presented by treatment arm:

- Overview of all treatment-emergent adverse events (TEAEs)
- Incidence of all treatment-emergent adverse events (TEAEs) by system organ class and preferred term
- Incidence of all treatment-emergent adverse events (TEAEs) by system organ class, preferred term, and maximum severity
- Incidence of all serious adverse events (SAEs) by system organ class and preferred term
- Incidence of treatment-related TEAEs by system organ class and preferred term
- Incidence of treatment-related TEAEs by system organ class, preferred term, and maximum severity
- Incidence of treatment-related serious adverse events (SAEs) by system organ class and preferred term
- Incidence of most common >5% TEAEs in any one treatment group by preferred term only
- Listing of all treatment-related adverse events
- Listing of all treatment-related serious adverse events (SAEs)
- Listing of discontinuations: Subjects who discontinued from the study due to any adverse event
- Listing of deaths: Subjects who died of any cause during the study

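### SAP 6.3.2: when only the month of an AE start is missing, the same-year rule dates an on-treatment AE that begins after a month end before first application, so it is not a TEAE by onset

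*SAP*

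**What the plan says.** SAP 6.3.2 treats partial start dates case by case. With day and year known and month missing, "If only the month is missing then the imputed month will be the month of the initial dressing/treatment application". This branch is for an AE in the calendar year of first application; for an AE in another year the rule assigns January. The recorded day is kept. The bullet does not compare the result with the date of first application or with the AE end date.

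The neighbouring bullets behave differently. If only the day is missing, the day of first application is used when the month matches. The first of the month is used when the month differs or when "the imputed day results in a start date after the end date". If day and month are both missing, the day and month of first application are used, with a similar end-date check. If start and end are both wholly missing, the event is taken as on-study and dated to first application.

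SAP 9.2 defines TEAEs as "adverse events with onset or worsening of pre-existing conditions on or after the initial dressing application through the course of the study". Protocol 8.1.3 says they "are those that first appear or worsen after the initial application of the assigned study treatment". Protocol 7.4 states: "The AE collection/reporting period will begin after the Subject has been randomized". Protocol 3.1.3 sets a treatment period of up to nine days, Day 0 to Day 9.

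**The concern.** Treatment lasts days rather than months, but many courses span a month end. For an event in the second calendar month, putting the month of first application with the recorded day moves the onset back by a whole month, to before treatment. The event is then not treatment-emergent by onset. The imputed date also conflicts with the collection rule, because no newly arising event should be on file with an onset weeks before randomisation.

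The result runs against the rest of SAP 6.3.2. An event with no date information at all stays treatment-emergent, while one with a known day and year can lose that status. AE incidence is the safety endpoint (Protocol 3.5, SAP 4.2) and about 30 subjects per arm are planned. One subject wrongly left out of a TEAE row therefore changes that arm's incidence by up to 1/30 = 3.3 percentage points.

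**Working it through.** The plan states no figure on this point, so there is none to reproduce. The check applies the rule as written.

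**Inputs.** Month-missing rule, both branches (SAP 6.3.2). TEAE onset on or after first application (SAP 9.2). Onsets from Day 0 to Day 9 at most (Protocol 3.1.3), with Day 0 to Day 6 as the short course.

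**Why a same-year crossing is always misdated.** Let first application fall on day *d* of a month with *L* days, and let the AE start *k* days later in the next month. The recorded day is *a* = *d* + *k* − *L*. The rule keeps *a* and assigns the month of first application, so:

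imputed onset − first application = *a* − *d* = *k* − *L*

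With *k* at most 9 and *L* at least 28, this is always negative.

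- First application 28 January, AE 3 February: *k* = 6, *L* = 31, imputed 3 January, 25 days before treatment.
- First application 28 March, AE 2 April: *k* = 5, *L* = 31, imputed 2 March, 26 days before treatment.

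**Year end.** First application 28 December, AE 2 January: the years differ, the rule assigns January, and the date is right.

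**How often.** For an onset on Day *k*, exactly *k* start dates before each month end lead to a crossing. Each month end therefore contributes 1 + … + 9 = 45 start/onset pairs for Day 0–9, or 1 + … + 6 = 21 for Day 0–6. Eleven month ends lie within a calendar year. Enumerating every start date gave the same counts:

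| Year and window | All pairs | Same-year crossings | Of these, dated before treatment | Year-end crossings | Of these, dated before treatment | Share of all pairs misdated |
|---|---|---|---|---|---|---|
| 2019, Day 0–6 | 365 × 7 = 2555 | 11 × 21 = 231 | 231 | 21 | 0 | 9.0% |
| 2019, Day 0–9 | 365 × 10 = 3650 | 11 × 45 = 495 | 495 | 45 | 0 | 13.6% |
| 2020, Day 0–6 | 366 × 7 = 2562 | 231 | 231 | 21 | 0 | 9.0% |
| 2020, Day 0–9 | 366 × 10 = 3660 | 495 | 495 | 45 | 0 | 13.5% |

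Pairs with no crossing were never misdated. Of all crossings, 495/540 = 91.7% are misdated.

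**Sensitivity to onset day.** In a 365-day year the share for a given onset day is 11*k*/365: 3.0% on Day 1, 18.1% on Day 6 and 27.1% on Day 9. Early onsets bring the overall figure down and late onsets raise it.

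**Scale.** Out of ten AEs that start on treatment and lack only the month, about one would be misdated (10 × 0.090 = 0.9 to 10 × 0.136 = 1.4).

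**The case against.** **The trigger is unlikely.** Subjects are expected to be inpatients, AEs are assessed at each visit with a start date recorded, serious events are reported within 24 hours of awareness, and monitors resolve discrepancies with the site. A known day and year with an unknown month should be rare, and a pre-treatment onset would invite a query. This stands and limits the impact. It does not make the rule correct.

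**Another bullet might rescue the event.** SAP 6.3.2 dates an AE with a missing start and a complete end date on or after first application to first application. Read to cover partial dates, it would catch some of these events. The reading is possible but less natural: separate bullets already deal with partial dates, and they would be largely redundant whenever an end date was known.

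**The day-missing check would not help.** It catches a start after the end date, whereas here the start is too early. That is right; the missing safeguard is a comparison with first application.

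**Stronger readings that the documents do not support.**
- A reader might infer that the rule always uses the month of first application. The January branch makes year-end crossings correct.
- A reader might infer that the event vanishes from all safety output, serious events included. An event recorded as worsening on treatment can still qualify. In SAP 9.2 the table of all serious events, and the listings of treatment-related events, discontinuations and deaths, are not worded as TEAE-only (Protocol 8.3.7 does specify treatment-emergent serious events).
- A reader might infer that the error can only remove events. A record from 28 March with the month missing, in a subject first treated on 3 April, would be dated 28 April. Collection after randomisation makes such records unlikely, but the text does not exclude them.
- A reader might take the 20% to 30% of courses that cross a month end (6/30.44 = 19.7%, 9/30.44 = 29.6%) as the share of AEs affected. That is a share of subjects; the share of onsets is 9% to 14%.

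**Conclusion.** Wrong as written, low impact. For any month end other than 31 December, an AE that starts on treatment after that month end and lacks only the month is dated before first application. It is therefore not counted as a TEAE by onset, against the protocol's own collection rule. This follows from the text and needs no distributional assumption.

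The 9% to 14% assumes uniform start dates, uniform onset days over Day 0–6 or Day 0–9, and that the partial-date bullet governs. It applies only to AEs missing the month alone. The documents do not say how many there are, so it is not a forecast of lost events. No effect on the trial's safety conclusion is shown.

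**What to change.** Add one sentence to SAP 6.3.2 for AEs. If an imputed start date falls before first application and the end date does not show that the AE ended before first application, use the next month when that date falls within the study period and is not after the AE end date; otherwise use the date of first application.

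In the 28 January example this gives 3 February, Day 6. Dates with no crossing and December/January dates already fall on or after first application, so they do not change. The cost is one sentence in the SAP and about one line of code, to be settled before database lock. No data collection or clinical procedure is affected.
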